10.3.5 Reporting of AESIs, SAEs, and Pregnancies

10.3.5.1 Events that Occur Before Study Drug Initiation

After informed consent has been obtained, but before initiation of study drug, only SAEs caused by a protocol-mandated intervention should be reported. The Serious Adverse Event /Adverse Event of Special Interest Reporting Form provided to Investigators should be completed and submitted to the Sponsor or its designee immediately (ie, ≤24 hours after learning of the event), either by faxing or by scanning and emailing the form using the fax number or email address provided.

Contacts for 24-hour emergency reporting can be found on Section 10.3.3.

10.3.5.2 Events that Occur after Study Drug Initiation

After initiation of study drug, AESIs, SAEs, and pregnancies will be reported until end of study at Day 115 or Early Termination. Investigators should record all case details that can be gathered immediately (ie, within 24 hours after learning of the event) on the Adverse Event eCRF and submit the report via the electronic data capture (EDC) system. A report will be generated and sent to Safety Risk Management by the EDC system.

In the event that the EDC system is unavailable, the Serious Adverse Event/Adverse Event of Special Interest Reporting Form provided to Investigators should be completed and submitted immediately (ie, ≤24 hours after learning of the event), either by faxing or by scanning and emailing the form using the fax number or email address provided in Section 10.3.5.1. Once the EDC system is available, all information will need to be entered and submitted via the EDC system.

10.4 Appendix 4: Toxicity Management

The toxicity management of AEs and AESIs includes safety monitoring (review of AEs on an ongoing basis and periodic review of safety by the external IDMC) and may include interruption of study drug dosing with appropriate clinical management if applicable and discontinuation of participants from study drug. The management of specific laboratory parameters is described below (Section 10.4.1).

10.4.1 Management of Hepatotoxicity

For elevations in ALT or AST, the Investigator should assess the participant for potential druginduced liver injury and apply the standard of care for medical evaluation and treatment following any local guidelines. All abnormal laboratory tests considered clinically significant by the Investigator will be followed to a satisfactory resolution.

For elevations in ALT or AST >2×ULN in participants with normal levels at baseline and any elevation in ALT or AST >3×ULN, obtain repeat ALT, AST, ALP, and total bilirubin within 48 to 72 hours*. Specific toxicity management guidelines are as follows:

- Discontinue study drug if confirmed ALT or AST >3×ULN by repeat testing with new sample AND a total bilirubin >2×ULN (with no evidence of hemolysis and an ALP value <2×ULN or not available)
- Discontinue study drug if confirmed ALT or AST >3×ULN by repeat testing with new sample along with appearance of fatigue, nausea, vomiting, right upper quadrant pain, or tenderness, fever, rash, and/or eosinophilia (>5%)
- If confirmed ALT or AST >3×ULN but ≤5×ULN, total bilirubin ≤2×ULN and participant is asymptomatic, study drug may be continued after consultation with the Sponsor and CRO Medical Monitor
- If confirmed ALT or AST >5×ULN but ≤10×ULN, total bilirubin ≤2×ULN, hold study drug
 until ALT or AST ≤5×ULN⁺; study drug may be restarted only if a cause other than the study
 drug has been established and if liver test returns to baseline. Rechallenge must be in
 consultation with Sponsor and CRO Medical Monitor. If abnormalities worsen after drug is
 restarted, study drug must be discontinued.
- Discontinue study drug if confirmed ALT or AST >10×ULN

Obtain repeat ALT, AST, ALP, and total bilirubin approximately every 3 days following receipt of previous laboratory results until ALT and AST are at or below approximate baseline levels for the participant. The frequency of retesting may be decreased to once a week or less if abnormalities are stabilized and participant is asymptomatic. If ALT and/or AST abnormalities worsen or remain >5×ULN for ≥14 consecutive days, study drug should be discontinued.

**In addition to repeating measurements of ALT, AST, ALP, and total bilirubin for suspected cases of potential drug-induced liver injury, additional laboratory tests should include, but are not limited to; albumin, creatine kinase, direct and indirect bilirubin, gamma-glutamyl transferase, and prothrombin time/international normalized ratio. Consideration should also be given to drawing a separate tube of clotted blood and an anticoagulated tube of blood for further testing, as needed, for further contemporaneous analyses at the time of the recognized initial abnormalities to determine alternative etiology.

⁺A detailed history including relevant information (eg, review of ethanol, acetaminophen/paracetamol [either by itself or as a coformulated product in prescription or over-the-counter medications], recreational drug use, supplement [herbal] use and consumption, family history, sexual history, travel history, history of contact with a jaundiced person, surgery, blood transfusion, history of liver or allergic disease, and potential occupational exposure to chemicals) should be collected. Further testing may be warranted (such as testing for acute viral hepatitis (A, B, C, D, and E) infection, liver imaging (eg, biliary tract), or serum drug levels (eg, acetaminophen/paracetamol). The Investigator should contact the Sponsor to discuss the management of a participant when an alternative etiology has been determined. The alternative etiology should be documented appropriately in the eCRF. Study drug should be discontinued if no alternative etiology can be found.

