7.1 Discontinuation of Study Drug

Participants will be prematurely discontinued from study drug for any of the following reasons:

- Participant experiences an AE as described below:
 - o Any Common Terminology Criteria for Adverse Events (CTCAE) Grade 3 and above AE that is assessed as related to study drug and/or no alternative etiology is found.
 - Any CTCAE Grade 2 AE that is assessed as related to study drug and/or no alternative etiology is found, is persistent, and falls into any of the following System Organ Classes: "Blood and Lymphatic Disorders" or "Cardiac Disorders".

If the event is deemed to be not related to study drug by the Investigator, the subject may continue study drug upon approval by the CRO Medical Monitor and Sponsor.

- Any AE, laboratory abnormality or intercurrent illness that, in the opinion of the Investigator
 or Sponsor, indicates that continued participation in the study is not in the best interest of the
 participant
- Clinical laboratory value meeting any of the following criteria:
 - Hepatotoxicity as described in Section 10.4.1
 - O Absolute neutrophil count <500 cells/μL, confirmed by repeat testing with new sample
- Development of erythrodermic, guttate psoriasis
- Participants who develop malignancy other than nonmelanoma skin cancer or carcinoma insitu of the cervix must be discontinued from study drug; information including histopathological results should be queried for the confirmation of the diagnosis
- Participant who develops active TB or pulmonary nontuberculous mycobacterial infection during the study
- Newly diagnosed IBD during the study must be prematurely discontinued from study drug
 and be followed-up until resolution of active IBD symptoms; participant should be referred,
 as appropriate, to a health care professional treating IBD, such as a gastroenterologist
- Participants must be referred immediately to a mental health professional (eg, locally licensed psychiatrist, psychologist, or master's level therapist) and must be withdrawn from the study for:
 - Active suicidal ideation as indicated by a positive response ("Yes") to Question 5 of the "Since Last Visit" version of the C-SSRS
 - o Any suicidal behavior since last visit

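### Protocol 10.4.1 orders a hold at ALT/AST >5 to ≤10×ULN when bilirubin is ≤2×ULN, but no bullet orders a hold or stop at the same ALT/AST when bilirubin is >2×ULN with ALP ≥2×ULN or hemolysis

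*Protocol*

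**What the plan says.** Protocol Section 10.4.1 asks for a repeat test within 48 to 72 hours and then gives five bullets. In order, for confirmed ALT or AST:

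1. Above 3×ULN: discontinue, subject to the condition "AND a total bilirubin >2×ULN (with no evidence of hemolysis and an ALP value <2×ULN or not available".
2. Above 3×ULN with any of a list of symptoms, or eosinophilia above 5%: discontinue, at any bilirubin.
3. A conditional permission: "If confirmed ALT or AST >3×ULN but ≤5×ULN, total bilirubin ≤2×ULN and participant is asymptomatic, study drug may be continued after consultation".
4. The hold: "If confirmed ALT or AST >5×ULN but ≤10×ULN, total bilirubin ≤2×ULN, hold study drug". On restarting, "study drug may be restarted only if a cause other than the study" drug has been established and liver tests are back to baseline.
5. Above 10×ULN: discontinue, at any bilirubin.

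After the bullets comes a persistence rule: "If ALT and/or AST abnormalities worsen or remain >5×ULN for ≥14 consecutive days, study drug should be discontinued". A footnote on work-up, whose marker sits on bullet 4, ends: "Study drug should be discontinued if no alternative etiology can be found". The liver item in the Section 7.1 stopping list reads "Hepatotoxicity as described in Section 10.4.1" and adds no threshold of its own.

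**The concern.** Bullets 1 and 4 split on bilirubin at 2×ULN but do not meet. Bullet 4 lapses once bilirubin exceeds 2×ULN. Bullet 1 takes over only when neither hemolysis nor raised ALP offers another explanation for the bilirubin. Between them lies a participant whose ALT/AST alone would have required a pause and whose bilirubin is now higher, yet for whom no bullet orders a hold or stop. The written rule becomes less strict as the liver picture worsens.

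Section 2.4 says liver tests are monitored to reduce the risk of drug-induced liver injury. It also records that earlier dosing in psoriasis lasted up to 28 days, against 84 here. With 60 to 65 sites, a threshold missing from the rule invites uneven handling while ALP or hemolysis is being explained.

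**Working it through.** The plan has no figure to reproduce here. The check runs the five bullets over every combination of bilirubin, ALP and hemolysis, for confirmed ALT/AST >5 to ≤10×ULN and no bullet-2 feature (no listed symptom, no eosinophilia above 5%).

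| ALP | Hemolysis | Bilirubin ≤2×ULN | Bilirubin >2×ULN |
|---|---|---|---|
| <2×ULN | no | hold (bullet 4) | discontinue (bullet 1) |
| <2×ULN | yes | hold (bullet 4) | no bullet |
| ≥2×ULN | no | hold (bullet 4) | no bullet |
| ≥2×ULN | yes | hold (bullet 4) | no bullet |
| not available | no | hold (bullet 4) | discontinue (bullet 1) |
| not available | yes | hold (bullet 4) | no bullet |

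All 6 combinations are held at the lower bilirubin. At the higher bilirubin 2 become discontinuations and 4 match nothing. Leaving out the two rows with ALP unavailable, 4 holds become 1 discontinuation and 3 without a bullet. These count rule combinations; they are not risks.

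An example: ALT 8×ULN, ALP 2.2×ULN, no hemolysis, no bullet-2 feature.
- At bilirubin 1.5×ULN, bullet 4 holds drug.
- At 2.5×ULN, bullet 1 fails on ALP, bullet 2 on the absence of symptoms and eosinophilia, bullets 3 and 4 on bilirubin, and bullet 5 on ALT.

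The other bands do not show this inversion. Above 10×ULN, bullet 5 stops every combination. At >3 to ≤5×ULN the same bilirubin, ALP and hemolysis findings also match no bullet. But bullet 3 orders no hold at the lower bilirubin, so none is lost, and no bullet permits continuing at the higher bilirubin.

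Extra dosing relative to bullet 4, with ALT/AST stable above 5×ULN:
- Lower end: 0 days, if another provision is used at once.
- Upper end, with the 14-day clock starting at the first result above 5×ULN: bullet 4 itself needs a confirming repeat at 48 to 72 hours (2 to 3 days), so 14 − 3 = 11 to 14 − 2 = 12 days. That is 11/84 = 13% to 12/84 = 14% of treatment. At 8 tablets a day (Section 6.2) it is 88 to 96 tablets.
- Upper end, with the clock starting at confirmation: 14 days, 14/84 = 17%, 14 × 8 = 112 tablets.

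The upper ends assume that nothing worsens and nobody acts on the intervening retests. Retesting is about every 3 days, and may drop to weekly or less once values stabilize in an asymptomatic participant.

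**The case against.** The strongest reply is that the bullets are guidelines within a larger safety system and that the rest of the protocol covers this participant.

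- Section 7.1 requires a stop for a Grade 3 or higher AE that is related or has no alternative etiology. If the Investigator deems the event unrelated, dosing may continue only with approval from the CRO Medical Monitor and Sponsor.
- Section 7.1 also stops drug for any laboratory abnormality that the Investigator or Sponsor judges makes continuing against the participant's interest, and gives both general discretion.
- Section 10.4.1 opens with a duty to assess for drug-induced liver injury and apply the standard of care.
- Section 8.0 sends immediate safety concerns to the Sponsor.
- The etiology footnote leads to discontinuation if no other cause is found and to Sponsor contact if one is.
- Section 10.4.2 interrupts dosing for hemoglobin below 8 g/dL, or a fall of at least 3.0 g/dL without another cause. This catches some hemolysis cases.
- The combination is rare, and Section 5.2 excludes participants with raised liver tests or hepatic impairment at entry.

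Much of this stands. A reader might infer that such a participant simply stays on drug at the site's discretion. The documents do not support that: the Section 7.1 approval step and the Sponsor's own power to stop take the decision beyond the site.

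What does not stand is that these provisions replace the hold. The Grade 3 route depends on the finding being reported as an AE, graded and attributed. The best-interest stop, the standard-of-care sentence and the Section 8.0 discussion rest on judgment. The footnote is attached to a bullet this participant does not meet, and acts only after a work-up. The hemoglobin rules miss milder hemolysis and raised ALP without hemolysis. The persistence rule waits for worsening or 14 days. None orders a prompt hold on the liver values themselves.

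It may also be said that the ALP and hemolysis exception is deliberate. It may well be, as a reason not to discontinue permanently under bullet 1. It does not explain why a temporary hold required at lower bilirubin should fall away.

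**Conclusion.** The gap is real and narrow: ALT/AST >5 to ≤10×ULN, bilirubin >2×ULN, ALP ≥2×ULN or hemolysis, and no bullet-2 feature. There the bulleted rule is weaker than at lower bilirubin. It is worth correcting because it is a stated safety rule and the correction is one line.

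The likely effect is small. Extra dosing runs from 0 to about 11–12 days, or 14 at most, depending on when the persistence clock starts and on values staying stable. Very few participants would be affected; the documents give no rate.

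Two further inferences are not supported. The 14-day, 112-tablet figure is a ceiling, not an expected excess. Nor does the unmatched part of the >3 to ≤5×ULN band show that a mandatory hold is missing there; adding one would be a clinical preference beyond the inconsistency.

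**What to change.** Leave the five bullets as they are and add one to Section 10.4.1, worded for example:

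> For confirmed ALT or AST >5×ULN and ≤10×ULN with total bilirubin >2×ULN, where bullets 1 and 2 are not met (that is, ALP ≥2×ULN or evidence of hemolysis): hold study drug and consult the Sponsor and CRO Medical Monitor. Restart only once a cause other than study drug is established and liver tests, including total bilirubin, are back to baseline.

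This covers all 4 unmatched combinations in the table (3 without the unavailable-ALP rows) and overlaps no existing bullet. A separate bullet also avoids stretching bullet 4's hold endpoint, which looks only at ALT/AST, to participants with raised bilirubin. The >3 to ≤5×ULN band stays with the existing consultation and discretion rules.

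The cost is one line, by clarification letter or at the next amendment. No new test is needed, since ALT, AST, ALP and bilirubin are already repeated. Bilirubin that recovers after ALT/AST may need an occasional extra draw, because the frequent-retest rule ends when ALT/AST reach baseline. The downside is a few more holds. Some could become discontinuations if the Section 10.4.2 rule on interruptions longer than 7 consecutive days is applied to liver holds.

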10.4.2 Management of Select Laboratory Abnormalities

For any given laboratory abnormality, the Investigator should assess the participant and apply the standard of care for medical evaluation and treatment following local guidelines as appropriate. Specific toxicity management guidelines for abnormal laboratory values are described below. All abnormal laboratory tests that are considered clinically significant by the Investigator will be followed to a satisfactory resolution. Repeat testing to confirm the abnormality must occur as soon as possible. If a participant experiences a study drug interruption >7 consecutive days during Days 15 through 85, the Sponsor or CRO Medical Monitor should be notified and study drug should be discontinued.

Hemoglobin

- If hemoglobin <8 g/dL: interrupt study drug dosing and confirm by repeat testing with a new sample
- o If hemoglobin decreases ≥3.0 g/dL from Baseline without an alternative etiology: interrupt study drug dosing and confirm by repeat testing with new sample
- o If hemoglobin decreases ≥3.0 g/dL from Baseline and an alternative etiology is known: the participants may remain on study drug at the Investigator's discretion
- o If confirmed: continue to withhold study drug until hemoglobin value returns to normal reference range or its Baseline value

Absolute neutrophil count

- If confirmed <1000 cells/μL by repeat testing with new sample: interrupt study drug dosing until absolute neutrophil count value returns to normal reference range or its Baseline value
- o If confirmed <500 cells/μL by repeat testing with new sample: discontinue study drug

Absolute lymphocyte count

 If confirmed <500 cells/μL by repeat testing with new sample: interrupt study drug dosing until absolute lymphocyte count returns to normal reference range or its Baseline value

Platelet count

o If confirmed <50,000 platelets/μL by repeat testing with new sample: interrupt study drug dosing until platelet count returns to normal reference range or its Baseline value

• Serum Creatinine

- o If serum creatinine is >1.5× the Baseline value and >ULN: repeat the test for serum creatinine (with participant in an euvolemic state) to confirm the results; if the results of the repeat testing still meet this criterion; interrupt study drug and restart study drug once serum creatinine returns to ≤1.5× Baseline value and ≤ULN
- o If confirmed serum creatinine ≥2 mg/dL: interrupt study drug and restart study drug once serum creatinine returns to normal reference range or its Baseline value

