Participants with mild to moderate renal impairment will be allowed to participate in the study, as data from Study DCE-806101 demonstrated that <3% of the dose was eliminated by the renal pathway. In addition, data from the radiolabeled mass-balance study in rats demonstrated that 4.27% of the dose was excreted by renal pathways, while 90% of the dose was excreted by feces. It is anticipated that renal impairment will have minimal effect on DC-806 exposure since the fraction of DC-806 eliminated unchanged in urine (F_e) is below the 0.3 limit set by FDA guidance (US Food and Drug Administration 2020).

Safety in this study will be assessed through the medical review of AEs, vital signs, 12-lead ECGs, clinical laboratory data (hematology, clinical chemistry, urinalysis), and physical examination findings. Nonclinical data have identified small ECG elevations at high doses that have not been observed in clinical studies; nevertheless, ECGs will be monitored during the study. An external IDMC will review unblinded safety data on a periodic basis during the study.

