- 7. History or evidence of active infection (including but not limited to COVID-19 infection) and/or febrile illness within 7 days, serious infections leading to hospitalization and intravenous antibiotic treatment within 90 days, or serious infection requiring antibiotic treatment within 30 days before the first dose of study drug
- 8. History of malignancy or lymphoproliferative disease except resected cutaneous squamous cell or basal cell carcinoma that has been treated without recurrence
- 9. Participant has previously received a solid organ transplant
- 10. Presence of active suicidal ideation, or positive suicide behavior using the "Baseline /Screening" version of the C-SSRS and with either of the following criteria:
 - History of suicide attempt (including an actual attempt, interrupted attempt, or aborted attempt) within 5 years before the Screening visit; participants with a history of a suicide attempt >5 years ago should be evaluated by a mental healthcare professional (eg, locally licensed psychiatrist, psychologist, or master's level therapist) before enrolling into the study
 - Suicidal ideation in the past month before the Screening visit as indicated by a positive response ("Yes") to either Question 4 or Question 5 of the "Baseline/Screening" version of the C-SSRS at Screening
- 11. History or evidence of hepatic impairment (eg, history or presence of ascites, encephalopathy, prolonged prothrombin time, hypoalbuminemia, or hyperbilirubinemia); history of any current serious or unstable illnesses including renal, gastrointestinal, respiratory, cardiovascular (including ischemic heart disease), endocrinologic, neurologic, psychiatric, immunologic, or hematologic disease or other conditions that, in the Investigator's opinion, could interfere with the analyses of safety and efficacy in this study
- 12. Have undergone major surgery within 12 weeks before the first dose of study drug or planned to be performed during the study (eg, hip replacement, aneurysm removal, stomach ligation) as assessed by the Investigator
- 13. Have a history of alcohol or substance abuse within 6 months before the first dose of study drug that in the opinion of the Investigator will preclude participation in the study
- 14. History of an allergic reaction or hypersensitivity to constituents of the study drug (and its excipients) and/or other products in the same class

Prior/Concomitant Therapy

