- 24. Received an experimental antibody or biologic therapy within the previous 6 months or 5 half-lives (whichever is longer), or received any other experimental therapy or new investigational agent within 30 days or 5 half-lives (whichever is longer) before the first dose of study drug, or is currently enrolled in an investigational study
- 25. Systemic use of known strong and moderate CYP3A4 inhibitors or strong CYP3A4 inducers from Screening through the end of the study (refer to Section 0)

Diagnostic Assessments

- 26. A 12-lead ECG at Screening that demonstrates clinically significant abnormalities or criteria associated with QT interval abnormalities, including prolongation of QTcF interval (>500 msec)
- 27. Laboratory values meeting the following criteria within the Screening period before the first dose of study drug:
 - Serum AST ≥2×ULN
 - Serum ALT ≥2×ULN
 - Serum total, direct, or indirect bilirubin ≥2.0 mg/dL; except for participants with isolated elevation of indirect bilirubin relating to a confirmed diagnosis of Gilbert syndrome
 - Serum albumin ≤3.5 g/dL
 - Prothrombin time ≥4 seconds or International Normalized Ratio ≥1.7
 - Estimated GFR by simplified 4-variable MDRD formula <45 mL/min/1.73m²
 - Total white blood cell count <3000/μL
 - Absolute neutrophil count <1500/μL
 - Platelet count <100,000/μL
 - Hemoglobin <9 g/dL
- 28. In the opinion of the Investigator or Sponsor, have any uncontrolled clinically significant laboratory abnormality that would affect interpretation of study data or the participant's enrollment in the study

Other Exclusion Criteria

- 29. Participants who are incapacitated, prisoners or involuntarily incarcerated, in compulsory detention for treatment of either a psychiatric or physical illness, or in other situations that render the participant vulnerable according to local regulations
- 30. Participants who are employees of the Sponsor or third-party organizations involved in this study or are Investigator-site personnel directly affiliated with this study and/or their immediate families (defined as a spouse, parent, child, or sibling, whether biological or legally adopted)

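### Protocol 10.4.2: the first serum creatinine rule has no return-to-Baseline restart, so an eligible participant whose Baseline exceeds ULN stays on hold after full recovery

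*Protocol*

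**What the plan says.** Protocol Section 10.4.2 has two creatinine bullets, called here the lower and the upper rule.

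- **Lower rule.** Trigger: "If serum creatinine is >1.5× the Baseline value and >ULN", confirmed on repeat. Restart: "restart study drug once serum creatinine returns to ≤1.5× Baseline value and ≤ULN".
- **Upper rule.** Trigger: a confirmed value of 2 mg/dL or more. Restart: "restart study drug once serum creatinine returns to normal reference range or its Baseline value".

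The hemoglobin, neutrophil, lymphocyte and platelet rules in the same section end their holds on the same terms as the upper rule: normal range or Baseline.

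The opening paragraph of 10.4.2 limits the length of any hold. After an "interruption >7 consecutive days during Days 15 through 85, the Sponsor or CRO Medical Monitor should be notified and study drug should be discontinued".

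On eligibility, Section 2.4 states: "Participants with mild to moderate renal impairment will be allowed to participate in the study". The numeric renal exclusion in Section 5.2 (criterion 27) is "Estimated GFR by simplified 4-variable MDRD formula <45 mL/min/1.73m²". There is no entry limit on creatinine itself. Criterion 11 covers "history of any current serious or unstable illnesses including renal, gastrointestinal" and other disease that the investigator thinks could interfere with the analyses. Criterion 28 covers those who "have any uncontrolled clinically significant laboratory abnormality that would affect interpretation of study data" or their enrollment. Baseline is the last non-missing value before the first dose (Protocol 9.3, SAP 4).

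**The concern.** A restart condition should be one that a recovered participant can meet. The lower rule requires creatinine to be at or below ULN. A participant who enters with creatinine above ULN can return exactly to the level at which dosing was considered acceptable and still be barred from restarting. Every other hold in the section would end at that point, including the one for the more severe creatinine tier.

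The hold does not stay open, because 10.4.2 says that drug should be discontinued once an interruption passes 7 consecutive days within Days 15 to 85. The outcome then depends on the restart wording:

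- **Drug restarted.** PASI after the interruption is used as reported (SAP 8.1.1.1, treatment policy).
- **Drug discontinued for an AE or laboratory abnormality.** Protocol 7.1 drops efficacy assessments from the later scheduled visits. SAP 8.1.1.1 classes the participant as a non-responder, by the composite strategy if the AE is related and otherwise through the missing Week 12 score.

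So a participant whose creatinine has fully recovered can lose treatment, and the chance of being counted as a responder, because of one missing clause.

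**Working it through.** The plan gives no figure to reproduce. The check is on the logic of the two rules.

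**Inputs.** B is the participant's Baseline. Triggers and restart conditions come from Protocol 10.4.2. The creatinine ULN is not in the documents (SAP 9.2 points to the Central Lab Manual). Where a number is needed I assume 1.0 to 1.1 mg/dL for women and 1.20 to 1.35 mg/dL for men. The general results below need only ULN < 2 mg/dL.

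**Step 1. Highest creatinine at which restart is allowed** (reading a return to a level as at or below it).

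- Lower rule: L1 = min(1.5 × B, ULN)
- Upper rule: L2 = max(ULN, B)

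**Step 2. Baseline above ULN.** Then 1.5 × B > B > ULN, so L1 = ULN, which is below B. The lower rule requires creatinine to fall below the participant's own Baseline. L2 = B, so the upper rule allows restart at Baseline.

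**Step 3. When the lower rule acts alone.** With B > ULN its trigger is a value above 1.5 × B. The upper rule stays silent below 2.0 mg/dL. Both hold only if 1.5 × B < 2.0, that is B < 2.0/1.5 = 1.33 mg/dL. At or above 1.33, every lower-rule hold is also an upper-rule hold. Under the assumed ULNs, the Baseline window in which the lower rule can act alone and block restart at Baseline is:

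| Assumed ULN (mg/dL) | Baseline window (mg/dL) |
|---|---|
| 1.0 | above 1.0, below 1.33 |
| 1.1 | above 1.1, below 1.33 |
| 1.20 | above 1.20, below 1.33 |
| 1.35 | none (1.35 > 1.33) |

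**Step 4. Examples.**

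- B = 1.15, assumed ULN 1.0 to 1.1, confirmed 1.80. 1.5 × 1.15 = 1.725, so 1.80 triggers the lower rule; 1.80 < 2.0, so the upper rule is silent. L1 = 1.0 to 1.1. Back at 1.15, restart is blocked.
- B = 1.50, assumed ULN 1.20 to 1.35, confirmed 2.1. 1.5 × 1.50 = 2.25, so only the upper rule triggers. L2 = 1.50. Back at 1.50, restart is allowed.
- B = 1.50, same ULN, confirmed 2.4. Both trigger. L1 = 1.20 to 1.35 and L2 = 1.50. A site that follows both rules cannot restart at 1.50.

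The first two examples show the inversion: a hold at 1.80 mg/dL cannot end at Baseline, while a hold at 2.1 mg/dL can.

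**Step 5. Do the two rules contradict each other?** For any B, max(ULN, B) ≥ ULN ≥ min(1.5 × B, ULN), so L2 ≥ L1. Meeting the lower rule always meets the upper one. A grid in 0.01 mg/dL steps (Baseline 0.40 to 1.70, current value 0.30 to 1.99, ULN 1.00, 1.10, 1.20 and 1.35) found no case in which the lower rule allows restart and the upper rule blocks it. The limits differ when B < ULN/1.5 or B > ULN, and coincide in between. With a low Baseline (B = 0.60, assumed ULN 1.1), L1 = 0.90 and L2 = 1.10; following both rules simply gives 0.90, which a recovered participant can reach. Only B > ULN produces a limit below Baseline.

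**The case against.** The strongest reply is that these are two separate holds, that a site can always comply with both by meeting the stricter one, and that being stricter with participants who enter above ULN is a legitimate choice. The first part stands. A reader might infer from the differing restart conditions that the section contradicts itself, or that it needs a precedence rule. The documents do not support that, as Step 5 shows, and the low-Baseline case is not a fault.

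The second part is weaker. Nothing in the protocol gives a reason for stricter handling of these participants. Section 2.4 expects renal impairment to have minimal effect on exposure. The more severe creatinine tier accepts return to Baseline, which is hard to square with deliberate caution in the milder tier.

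Three practical replies reduce the size of the point but do not remove it.

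- **Flexibility.** Section 10.4.2 calls its rules guidelines, refers to standard of care, and brings in the Sponsor or Medical Monitor once a hold exceeds 7 days. That leaves some room, but the stated action at that point is discontinuation, and Section 8.0 does not allow waivers or exemptions.
- **Few eligible participants.** Criteria 11 and 28 may remove some participants with Baseline above ULN. Neither bars stable impairment.
- **Other exits.** Section 7.1 separately discontinues a participant for a Grade 3 or higher AE that is related or has no alternative etiology, so some would stop whichever restart wording applied. Conversely, with Baseline only just above ULN, ordinary variation may bring a value to ULN or below in time to restart.

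**Conclusion.** The concern holds, and it is minor. The lower creatinine rule is faulty as written for participants whose Baseline exceeds ULN, because its restart limit lies below their own Baseline. This follows from the text. It rests on Baseline above ULN being possible, which the admission of mild to moderate renal impairment without a creatinine ceiling supports. Exact mg/dL windows depend on the assumed ULNs; the 1.33 mg/dL bound does not.

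The documents do not say how many participants enter above ULN or how often such rises occur, and the count may be zero. For scale, one participant who would otherwise have responded moves an arm's Week 12 rate by 1/45 = 2.2 percentage points. A reader might infer a threat to the primary comparison. The documents do not support that: harm needs a Baseline above ULN, a confirmed 1.5-fold rise, and a level that stays above ULN for more than 7 days within the stated window. No power, alpha or analysis method changes.

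**What to change.** In the lower creatinine rule, allow restart once creatinine is at or below both 1.5 times Baseline and ULN, **or** has returned to the Baseline value. With B = 1.15 and assumed ULN 1.0, the restart limit moves from 1.00 to 1.15. With B = 1.50 and assumed ULN 1.20 to 1.35, it moves from 1.20–1.35 to 1.50. With B = 0.60 and assumed ULN 1.1, it stays at 0.90, so the 1.5-fold safeguard for low Baselines is kept.

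Optionally, put the same condition in the upper rule so that one restart condition covers both. The downside is a slightly stricter upper-rule restart when Baseline is below ULN/1.5 (0.90 in place of 1.10 in the last example), which following both rules already implies.

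The cost is one line in the next amendment or a clarification to sites. The SAP needs no change.
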